**Carolinas HealthCare System
Center for Liver Disease**

Spironolactone to prevent or delay calcineurin nephrotoxicity after liver transplantation

Title: Investigator initiated study of spironolactone to prevent or delay calcineurin nephrotoxicity in liver transplant recipients

Principal Investigator: [name]

Sub-Investigators:

[name]
[name]
[name], MD
[name], PA-C
[name], PA-C
[name]
[name]
[name]
[name]

1. Specific Aim:

- a. To determine if spironolactone decreases nephrotoxicity from calcineurin inhibitors in liver transplant recipients.
- b. To determine the best study of renal function in liver transplant recipients.

2. Background:

Chronic kidney injury affects up to 30% of liver transplant recipients after transplantation.

Nephrotoxicity from calcineurin inhibitors (CNIs- tacrolimus, cyclosporine) is the leading cause of chronic kidney injury after liver transplantation. Strategies to reduced kidney injury include minimizing exposure to CNI's by using combination immunosuppressive regimens, such as low dose CNI and mycophenolate mofetil. Other strategies include switching from CNI to Mammalian target of rapamycin (mTOR) inhibitor. However, there may be barriers to using low dose CNI or mTOR inhibitor such as increased rate of rejection, CMV infection, or increased cost. Spironolactone is an antagonist of aldosterone, acting primarily through competitive binding of receptors at the aldosterone-dependent sodium-potassium exchange site in the distal convoluted renal tubule. Animal models of CNI nephrotoxicity demonstrate decreased nephrotoxicity and kidney fibrosis in rodents treated with spironolactone. Small studies have demonstrated improved creatinine clearance in liver transplant recipients treated with spironolactone. In these studies spironolactone at low doses was well tolerated with acceptable rates of hyperkalemia.

3. Study design:

Randomized clinical trial of spironolactone versus no spironolactone in liver transplant recipients on calcineurin inhibitors (tacrolimus or cyclosporine).

- Subjects that are 3 weeks to 6 months post liver transplant will be screened for the study. After eligibility is established and informed consent document has been signed by the patient or representative, subjects will be randomized to spironolactone 25 mg daily, or no treatment. Non-English only speaking subjects will be consented with an interpreter. A total of 36 patients will be randomized (50/50), 18 to treatment and 18 to standard of care. Subjects that do not wish to enroll or do not meet the criteria for the main study may choose to participate in the sub-study if they are not allergic to iodine and if their GFR is greater than 30 ml/min. 36 subjects may be enrolled in the sub-study to compare the currently used method of evaluating kidney function based on serum creatinine to other measures of creatinine clearance and kidney filtration rate (iothalamate GFR, 24 hour urine for creatinine clearance and protein, serum cystatin C, basic metabolic package and serum albumin).

Inclusion Criteria

- Liver transplant within 3 weeks to 6 months of study enrollment.
- Age 18-75 years old
- Proteinuria less than 3 g/24 hours
- Creatinine Clearance greater than 30 ml/min
- Negative pregnancy test for women of child bearing potential

Exclusion Criteria

- Patients on angiotensin converting inhibitors or angiotensin receptor blockers, digoxin, other drugs associated with hyperkalemia (dapsone can be substituted for sulfamethoxazole if needed at the discretion of the investigator)
- Potassium greater than 5.2 meq/L on screening labs, one occasion in a non-hemolyzed specimen,
- Prior intolerance to spironolactone
- Factors, that in the opinion of the investigator, would interfere with subject's compliance with the study
- Retransplantation
- Combined organ transplant-i.e. liver kidney, liver-heart
- Subjects who are anticipated to be placed on sirolimus or everolimus due to underlying condition (i.e. patients with HCC outside Milan criteria or with vascular invasion). Other

renal sparing protocols are allowed in including initial treatment with simulect, CNI reduction with mycophenolate mofetil

- Allergic to iodine

Patients will be monitored by SOC transplant protocol for up to 2 years.

For those subjects on treatment, if potassium stays less than 5.2 meq/L after 1 month on treatment, spironolactone may be increased to 50 mg daily at the discretion of the investigator.

4. Statistical analysis:

Mean GFR will be compared using unpaired Students' T test between groups and paired Students' t test within groups. If creatinine clearance is not normally distributed a nonparametric test will be used (Wilcoxon rank sum test) to compare creatinine clearance between groups. Sample size: 16 subjects in each group will be needed to detect a 10 ml difference in creatinine clearance with a power of 0.5 at $p \leq 0.05$.

5. Outcomes:

Primary outcome

- Change in creatinine clearance from screening to 1 year post randomization based on iothalamate GFR (glomerular filtration rate).
- Renal function tests will be compared to the iothalamate GFR to determine which best approximates the Glofil results.

Secondary outcomes

- Patient survival
- Graft Survival
- 6 month and 18 month creatinine clearance
- Dialysis
- Hyperkalemia ($>5.5 \text{ mEq/L}$)
- Proteinuria as defined by $> 3 \text{ g/24h}$

- Discontinuation for adverse events
- Conversion to renal sparing immunosuppressive regimen
- Number of subjects requiring sodium bicarbonate (NaHCO₃)
- Calculation of CKD-EPI, CKD-EPI Cystatin, CKD-EPI-Cystatin-Creatinine, MDRD-4, MDRD-6 and 24 hour urine creatinine clearance at screening and 6, 12, 18, and 24 months. Comparison of the currently used method of evaluating kidney function based on serum creatinine to other measures of creatinine clearance and kidney filtration rate (CKD-EPI, CKD-EPI Cystatin, CKD-EPI-Cystatin-Creatinine, MDRD-4, MDRD-6, 24 hour urine creatinine clearance and iothalamate GFR).

6. Study Calendar of Events

	Screening	Randomization	Day 7	Wk 2	Wk 3	Wk 4	MONTHLY until month 24	MONTHS 6,12,18,24
	45 days from screening	±2 days	±2 days	±2 days	±2 days	±5 days	±2 weeks	
History and physical	X							
Vitals signs (if recorded as part of the standard of care visit)	X	X	X	X	X	X	X	
ECG	X							
CHEM-7	X	X	X	X	X	X*		
Albumin level (standard of care lab within 30 days)	X						X	
24 HR creatinine clearance and 24 hour urine protein							X	
Cystatin C		X						X

		[name]					
		ONLY 12, 24 MONTHS					
Iothalimate GFR **		X					
Adverse events		X					
BLOOD FOR DNA ANALYSIS (Preferably collected at randomization, but may be collected at any post-randomization visit)		X					

*BMP weekly for 2 weeks if dose change in spironolactone or addition of NaHCO₃

**Depending in the budget a subset of subjects may undergo iothalimate scans at baseline and 1 year

7. Safety and Monitoring Plan

Subjects in the study are liver transplant recipients who are regularly followed with blood work and physician and nurse visits. Standard of care blood work includes a complete metabolic panel, complete blood count, and tacrolimus level. These labs are obtained twice a week the first week after discharge from the hospital, then weekly until week 12 after discharge, then every 2 weeks until month 6, then monthly until year 2.

Transplant pharmacist, [name], and nephrologist, [name], have agreed to be available to discuss adverse events, and for advice and to help manage electrolyte abnormalities.

8. Adverse Event Management

The risks to subjects on spironolactone treatment are hyperkalemia and hypertension. As stated above patients will be monitored after liver transplant regularly per liver transplant protocol that follows standard of care. Any unscheduled labs will be paid for by the study. Subjects may also develop gynecomastia which will be treated by dose reduction and if not effective discontinuation of the spironolactone.

Protocol of elevated potassium

- If subject on spironolactone 50 mg daily and potassium is greater than 5.5 mg/mL then dose reduce spironolactone to 25 mg daily, and recheck potassium in 5 days. If potassium remains greater than 5.5 meq/L then patient will be discontinued from the study.
- If subject is on spironolactone 25 mg daily and potassium is greater than 5.5 meq/L, the spironolactone will be discontinued for 7 days and the potassium level will be rechecked. If the potassium level continues to be greater than 5.5 meq/L, then the subject will be discontinued from the study at the discretion of the investigator. If the subject's potassium is within normal limits, the investigator may resume the spironolactone at the investigator's discretion.
- Sodium Bicarbonate is allowed for subjects with bicarb (CO₂) < 20 at 650 mg 2 pills twice a day for target bicarb 24 meq/L.

Treatment of hypertension

- Standard post-liver transplant protocol for hypertension will be followed with amlodipine as first line agent.
- Furosemide is allowed for hypertension or edema.
- Angiotensin converting enzyme inhibitors and angiotensin receptor blockers are contraindicated.

Most women undergoing liver transplant are post-menopausal. As part of standard of care, women are advised against pregnancy the first 3 years after liver transplant. Urine pregnancy testing will be offered to women who suspect pregnancy as part of standard of care.

9. DNA Analysis

Subjects will be asked to consent for collecting and storing blood for DNA analysis. If a subgroup of subjects derive a benefit from spironolactone their DNA will be analyzed for polymorphisms known to be associated with nephrotoxicity from tacrolimus.

10. Compensation

Study medication and study related visits, labs, and iothalamate scan will be paid for by the study. Standard of care visits will be billed to insurance. Subjects will be made aware of standard of care versus study related visits, labs, and charges. Liver transplant recipients are seen by a physician the first week after discharge from the hospital after the liver transplant, and weekly for the first month. Subjects are seen every 2 weeks the second and third month after liver transplant. Then subjects are seen 6 months, 9 months and 1 year, then annually after liver transplant. A stipend will be given to subjects that are required to return to the Transplant Center for a visit which is outside of the standard of care. If the subject travels 60 miles or less, the subject will receive a 25 dollar stipend. If the subject travels greater than 60 miles, the subject will receive a 50 dollar stipend.

References:

2. Bobadilla NA, Gamba G .New insights into the pathophysiology of cyclosporine nephrotoxicity: a role of aldosterone.Am J Physiol Renal Physiol. 2007 Jul;293(1):F2-9. Epub 2007 Apr 11. Review.

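### As written, the iothalamate sub-study rule waives the main study's lower age limit and pregnancy-test criterion, and nothing else in the protocol restores them

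*Combined protocol and SAP*

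**What the plan says.** The sub-study rule is in the opening paragraph of Section 3 (Study design). It names who may enter, "Subjects that do not wish to enroll or do not meet the criteria for the main study", and then the conditions: they "may choose to participate in the sub-study if they are not allergic to iodine and if their GFR is greater than 30 ml/min". Up to 36 subjects may be enrolled. The listed procedures are measurements of kidney function, iothalamate GFR among them; no study drug is given.

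The main-study Inclusion Criteria follow in the same section. They include "Age 18-75 years old", "Negative pregnancy test for women of child bearing potential" and "Creatinine Clearance greater than 30 ml/min". Iodine allergy is on the exclusion list. The pool to be screened is set by time since transplant alone: "Subjects that are 3 weeks to 6 months post liver transplant will be screened for the study".

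The only other text on pregnancy testing is in Section 8 (Adverse Event Management): "Urine pregnancy testing will be offered to women who suspect pregnancy as part of standard of care". The same paragraph says that most female transplant recipients are past menopause and that women are counselled against pregnancy for the first 3 years.

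**The concern.** The sub-study is open by design to people who fail the main-study criteria, and the rule does not say which criteria may be failed. A woman who fails because her pregnancy test is positive, or a recipient who fails because of being under 18, still satisfies the two stated conditions and so qualifies for the iothalamate procedure.

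At stake is participant protection. The protocol thought both criteria necessary for the main study, and the written sub-study rule sets them aside without comment. Staff enrol from the text, so an eligibility rule has to work as it is written.

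**Working it through.** No arithmetic beyond counting applies. The check sets the sub-study rule against each main-study criterion in Section 3, then looks for any text elsewhere that would restore what is missing.

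**Step 1. Which main-study criteria are restated for the sub-study?**

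| Main-study criterion (shortened) | Restated? | Nature |
|---|---|---|
| Time since transplant | No | Already covered by the screening sentence |
| Age 18 to 75 | No | Lower limit protects participants |
| Proteinuria limit | No | Shapes the trial population |
| Creatinine clearance above 30 ml/min | Yes, as GFR | Renal threshold |
| Negative pregnancy test | No | Protects participants |
| Drugs linked to hyperkalemia | No | Study drug or potassium |
| Potassium above 5.2 | No | Study drug or potassium |
| Past spironolactone intolerance | No | Study drug or potassium |
| Expected poor compliance | No | Shapes the trial population |
| Retransplantation | No | Shapes the trial population |
| Combined organ transplant | No | Shapes the trial population |
| Sirolimus or everolimus expected | No | Shapes the trial population |
| Iodine allergy | Yes | Fits the measurement procedure |

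There are 5 inclusion and 8 exclusion criteria, 13 in all. Two are restated, so 13 − 2 = 11 are not. Those 11 divide as follows: 1 covered by the screening sentence, 3 about the study drug or potassium, 5 that shape the trial population, and 2 that protect participants (1 + 3 + 5 + 2 = 11). The grouping is mine; the documents give no reasons for their criteria.

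**Step 2. Could the other criteria carry over by implication?** Not on this wording. The renal threshold and iodine allergy are already main-study criteria. If the whole list carried over, restating these two would be redundant, and admitting people who fail the list would contradict itself.

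**Step 3. Does any other section restore age or pregnancy status?**

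- The consent sentence in Section 3 is written for the randomized study, allows a representative to sign, and sets no adult-only limit.
- Sections 4 and 5 cover analysis and outcomes; neither adds a condition for entry.
- Section 8 offers pregnancy testing on suspicion, as standard care. That is not a condition for entering the sub-study.
- No section gives the sub-study an eligibility list of its own.

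**Step 4. How many subjects?** The documents give no count of women of child-bearing potential or of minors, so the number affected cannot be computed. The 36 places are only a ceiling. Section 8's remark on menopause and the advice against pregnancy point to few women, and nothing in the protocol says that the centre treats anyone under 18.

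**The case against.** The strongest reply is that the relaxation is deliberate and sensible. The sub-study gives no spironolactone, so criteria about potassium, interacting drugs or intolerance have no purpose there. The two conditions that were kept fit the measurement procedure. The pregnancy criterion may exist only because of the study drug: no section says why it is there or states a fetal risk from iothalamate. Minors are a remote possibility, since the protocol contains no paediatric procedure or assent process.

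Much of this stands. Waiving the drug-related and potassium-related criteria is reasonable, the reason for the pregnancy criterion is unstated, and the situation will be rare. These points limit how often the gap would matter and what may be asked of the sponsor. They do not close it: the rule expressly admits people who fail the criteria, and the protocol does not say that waiving these two was intended.

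Two stronger readings are tempting, and the documents do not support them:

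- A reader might infer that Section 8 contradicts the inclusion criterion, because it offers testing only on suspicion. The criterion governs entry, while Section 8 describes standard care, which can be read as applying after entry. Both can hold.
- A reader might infer from the lack of a pregnancy-test row in the Section 6 calendar that the test is not performed. The table is broken in the text available, and it also shows no screening mark for the 24-hour urine tests, although creatinine clearance and proteinuria are entry criteria. A missing row therefore proves little.

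**Conclusion.** The point holds in a limited form. The sub-study rule, taken as written, waives the lower age limit of 18 and the negative pregnancy test, and no other text restores them. It is a gap in participant protection that is cheap to close and likely to touch few subjects or none. The conclusion rests on a literal reading of the sub-study sentence and on the absence of a separate sub-study eligibility list in the protocol.

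Two larger claims should not be drawn from it:

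- One might say that the safeguard is bypassed for half of enrollment, since 36 / (36 + 36) = 50%. That figure measures the size of the sub-study, not exposure to the gap. The pregnancy criterion concerns only women of child-bearing potential, and those who enter because they declined the main study may meet all of its criteria.
- One might argue that pregnant women or minors would distort the comparison of kidney-function measures under Aim b. That needs a premise about how creatinine relates to GFR in these groups. The documents do not supply it, so the point is not made here.

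**What to change.** Reconcile the sub-study sentence in Section 3 with the Inclusion Criteria. Add a statement that the protocol's existing lower age limit and its existing pregnancy-test criterion also apply to entry into the sub-study. If the sponsor means to waive either one, say so in the same place and give the reason. The criteria about spironolactone and potassium can stay waived.

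The cost is a sentence of protocol text, a slightly smaller pool for the sub-study, and a urine test for a few women. No change to the sample size or the analysis follows.

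### The outcome year starts anywhere from 3 weeks to 6 months after transplant, and the planned between-group test makes no use of time since transplant

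*Combined protocol and SAP*

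**What the plan says.** Section 3 (Study design) opens screening over a wide window: "Subjects that are 3 weeks to 6 months post liver transplant will be screened for the study". The Inclusion Criteria repeat it: "Liver transplant within 3 weeks to 6 months of study enrollment". On allocation, section 3 says only "A total of 36 patients will be randomized (50/50), 18 to treatment and 18 to standard of care". It names no method, block size or stratification factor.

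Section 5 (Outcomes) gives the primary outcome as "Change in creatinine clearance from screening to 1 year post randomization based on iothalamate GFR (glomerular filtration rate". The clock is therefore tied to screening and randomization, not to the transplant date.

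Section 4 (Statistical analysis) plans this: "Mean GFR will be compared using unpaired Students' T test between groups and paired Students' t test within groups". If the data are not normal, "a nonparametric test will be used (Wilcoxon rank sum test) to compare creatinine clearance between groups". Neither test includes a covariate, and time since transplant appears nowhere in the analysis.

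Section 4 also states that "16 subjects in each group will be needed to detect a 10 ml difference in creatinine clearance with a power of 0.5", at a 0.05 level. It gives no SD and does not say whether the test is one- or two-sided.

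**The concern.** A subject who enters at 3 weeks contributes a year that includes early recovery and the first months of calcineurin inhibitor exposure. A subject who enters at 6 months contributes a year that includes neither. If untreated GFR change depends on where in the course the year starts, two things follow. Mixing early and late starters adds spread to the outcome. And with 18 per arm, the arms can by chance differ in mean entry time, which shifts the observed difference in this one trial. The plan reports power of only 0.5, so recoverable precision matters.

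The protocol offers indirect support that the periods differ: the section 7 laboratory schedule thins out from twice weekly after discharge to monthly after month 6. Time since transplant must also be known for every subject, because eligibility depends on it.

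**Working it through.** **1. What the outcome year covers.** Three weeks is 21/30.44 = 0.69 month. Earliest entrant: months 0.69 to 12.69. Latest entrant: months 6 to 18. Shared period: 12.69 − 6 = 6.69 months, or 6.69/12 = 56%. The section 6 calendar also carries the entry "45 days from screening". Its column is uncertain in the extracted table. If it is the allowed gap between screening and randomization, the change interval itself runs from 12 to about 13.5 months.

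**2. The plan's own figure.** With no SD stated, 16 per group cannot be reproduced independently. Solving for the SD that gives power 0.50 with n = 16 per group and a difference of 10 ml at 0.05 yields:
- two-sided: 13.97 (noncentral t) or 14.43 (normal approximation)
- one-sided: 16.81 (noncentral t) or 17.20 (normal approximation)

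I use 13.97. Check: SE = 13.97 × √(2/16) = 4.94; 10/4.94 = 2.02 against a critical t (30 df) of 2.04, so power is 0.50.

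**3. Chance imbalance in entry time** (assumption: entry uniform over the window; 18 per arm as randomized).
- SD of entry time = (6 − 0.69)/√12 = 1.53 months
- SE of the arm difference in means = 1.53 × √(2/18) = 0.51 month
- 95% limits = 1.96 × 0.51 = ±1.0 month
- Probability that the difference exceeds 0.5 month: 33%; 1 month: 5%

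**4. Is the between-group test valid?** Simulated trials with 18 per arm, no treatment effect and slopes of 1, 2 and 3 ml/min per month gave type I error of 0.051, 0.050 and 0.048 for the unadjusted t test.

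**5. Size for an assumed slope b** (ml/min difference in 1-year change per month of later entry; not in the documents).
- Spread across the window = b × 5.31
- 95% limits of the entry-time part of the arm difference = b × 1.0
- R² = (b × 1.53/13.97)²
- Adjusted SE = 13.97 × √(1 − R²) × √(2/16 × (1 + 1/28)), with 29 df. The factor 1 + 1/28 is the expected variance cost of estimating one covariate without forced balance: 1 + 1/(2n − 4), n = 16.

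Example, b = 2: R² = (3.07/13.97)² = 0.048; residual SD 13.63; SE = 13.63 × 0.360 = 4.90; 10/4.90 = 2.04 against a critical t of 2.05; power 0.505.

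| Slope b | Spread over window (ml/min) | 95% limits of entry-time part (ml) | R² | Power, adjusted, 16 per group |
|---|---|---|---|---|
| 0 | 0 | 0 | 0 | 0.49 |
| 0.5 | 2.7 | ±0.5 | 0.003 | 0.49 |
| 1 | 5.3 | ±1.0 | 0.012 | 0.49 |
| 2 | 10.6 | ±2.0 | 0.048 | 0.505 |
| 3 | 15.9 | ±3.0 | 0.108 | 0.53 |
| 5 | 26.6 | ±5.0 | 0.301 | 0.63 |

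Unadjusted power is 0.50 throughout. By the same formula, adjustment breaks even at a slope of about 1.75 (R² = 0.037). The spread across the window is then 1.75 × 5.31 = 9.3 ml/min, nearly the 10 ml target.

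**6. Comparison with ordinary sampling error.** The 95% range of the arm difference from all sources at 18 per arm is 1.96 × 13.97 × √(2/18) = ±9.1 ml. The limits in the table are a component of that range, not an addition to it.

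**The case against.** The strongest case on the other side is that this is an optional efficiency refinement whose benefit the documents cannot establish. Entry time is fixed before randomization, so it is balanced in expectation, and the t test already carries its variance. No GFR trajectory is given. The section 7 schedule is routine safety monitoring counted from hospital discharge, and it does not show that 1-year GFR change depends on entry month. At slopes of 1 or below, adjusting costs slightly more power than it returns. All of this stands, and it sets the weight of the point.

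A reader might also draw three stronger inferences that the documents do not support.
- *That simple randomization is used.* The method is not stated. Independent coin flips would give exactly 18/18 only 13% of the time, so fixed counts, if meant literally, suggest some restriction.
- *That the comparison is biased by enrolment time.* The simulated type I error argues against any systematic bias. What remains is chance imbalance in the realized trial: with a 1-month difference and a slope of 2, for example, the arm difference shifts by 2 ml.
- *That entry time adds a distortion of up to half the 10 ml target.* That figure needs a slope of 5, and the shift is already within the ±9.1 ml sampling range.

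The objection does not remove the gap itself. A baseline value known for every subject, plausibly related to outcome, is left out of the analysis, and adjusting for it only after seeing the data would be post hoc.

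**Conclusion.** The point holds as a matter of precision and chance imbalance, not of validity. The outcome year spans materially different post-transplant periods, with only 56% overlap at the extremes, and the planned between-group tests do not use that information.

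Its size is unknown. Over assumed slopes of 0.5 to 5 ml/min per month, the effect on power at 16 per group runs from a loss of about one point to a gain of about 13 points, and the clear gains need slopes of 3 or more. These figures rest on uniform entry, a linear relation, a two-sided test and the SD of about 14 inferred from the stated power. If the test were one-sided, the implied SD would be about 17 and entry time would explain a smaller share of it. Nothing here repairs a design with power of 0.5: even at an R² of 0.30, a power of 0.8 needs about 23 per arm (normal approximation, before the cost of the covariate).

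The change is worth considering; it is not a required correction.

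**What to change.** Pre-specify the primary between-group comparison in section 4 as a linear model (ANCOVA) for the 1-year outcome, with treatment group and weeks since transplant at randomization as terms. The entry window and sample size stay as they are. The Wilcoxon test, which takes no covariate, can remain as an unadjusted sensitivity analysis. State the randomization method in section 3, including whether allocation is blocked or stratified, since the text is silent on it.

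The cost is one degree of freedom, and about one point of power (0.50 to 0.49) if entry time turns out not to be prognostic. No new data are collected.

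Stratifying by early versus late entry in small permuted blocks is not recommended as a required change. The comparator is no treatment, so allocation is open, and small blocks within two strata of a 36-subject trial would make upcoming assignments easier to predict. The covariate obtains most of the precision without that risk.

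### The potassium exclusion is read on screening labs only, so the text permits randomizing a subject whose potassium at randomization is above the entry limit or above the level at which 25 mg is interrupted

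*Combined protocol and SAP*

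**What the plan says.** - **Entry limit (Section 3, Exclusion Criteria).** The potassium exclusion is "Potassium greater than 5.2 meq/L on screening labs, one occasion in a non-hemolyzed specimen". No other criterion mentions a potassium value.
- **Step to allocation (Section 3).** "After eligibility is established and informed consent document has been signed by the patient or representative, subjects will be randomized to spironolactone 25 mg daily"; the other arm receives no treatment. No re-check at randomization is described. On numbers: "A total of 36 patients will be randomized (50/50), 18 to treatment and 18 to standard of care".
- **Calendar (Section 6).** Screening and Randomization are separate columns. The row of visit windows begins with "45 days from screening". The CHEM-7 row carries marks at screening, at randomization and at the early visits. Its only footnote is "BMP weekly for 2 weeks if dose change in spironolactone or addition of NaHCO₃", which says nothing on eligibility.
- **Elevated potassium (Section 8).** "If subject is on spironolactone 25 mg daily and potassium is greater than 5.5 meq/L, the spironolactone will be discontinued for 7 days"; a recheck follows. A parallel rule covers 50 mg. Both rules address subjects already taking the drug.
- **Outcomes (Section 5).** Hyperkalemia above 5.5 mEq/L and discontinuation for adverse events are secondary outcomes. Nothing is said about values already raised at baseline.
- **Standard-of-care labs (Section 7).** Metabolic panels are drawn twice in the first week after discharge, "then weekly until week 12 after discharge, then every 2 weeks until month 6, then monthly until year 2". They are not linked to eligibility.

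**The concern.** Section 8 names hyperkalemia as a risk of spironolactone, and the entry limit exists to keep subjects with raised potassium off the drug. Entry is possible from 3 weeks after transplant, a period in which the protocol's own laboratory schedule is weekly or every two weeks. A result that may be 45 days old nevertheless decides entry, and the newer one, drawn at randomization, decides nothing.

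Two things are at stake. The first is safety: a subject above the sponsor's own limit can start the drug. The second is interpretation: a potassium above 5.5 that was present before the first dose could be recorded as an outcome event. In the treated arm it could also lead to interruption or discontinuation that the drug did not cause. With 18 per arm, one subject is 1/18 = 5.6% of an arm.

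**Working it through.** The plan states no figure on this point, so there is none to reproduce. The check is a reading of the rules together, followed by an illustration of size.

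**1. Is 45 days the screening-to-randomization window?** The calendar has eight columns: Screening, Randomization, Day 7, Weeks 2, 3 and 4, Monthly, and Months 6/12/18/24. The window row has seven entries: 45 days from screening, ±2 days four times, ±5 days, ±2 weeks. Screening needs no window relative to itself, and the seven entries fit the seven columns from Randomization onward. This is an inference from a damaged table, but a well-supported one.

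**2. Which rule acts on the randomization potassium?** Take a subject who passed at screening, for example with 4.9.

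| Potassium at randomization (meq/L) | Entry rule (>5.2, screening labs) | Section 8 rule (>5.5, on drug) | Hyperkalemia outcome (>5.5) |
|---|---|---|---|
| up to 5.2 | not applied; value within the limit | no | no |
| 5.3 to 5.5 | not applied; value exceeds the limit | no | no |
| above 5.5 | not applied; value exceeds the limit | met only once on 25 mg | value meets the definition; handling at baseline not stated |

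In the second row no rule acts at all. In the third row the first rule to act does so only after treatment has begun.

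**3. How many other results fall in the gap?** 45/7 = 6.4, so at most 6 weekly standard-of-care panels; 45/14 = 3.2, so about 3 on the two-weekly schedule. None is tied to entry.

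**4. Illustration of size.** All inputs are assumptions, because the documents give no potassium mean, SD or correlation. Let K1 (screening) and K2 (randomization) be bivariate normal with the same mean μ and SD σ and with correlation r. With a = (5.2 − μ)/σ and b = (c − μ)/σ,

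P(K2 > c | K1 ≤ 5.2) = [Φ(a) − Φ₂(a, b; r)] / Φ(a).

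Over μ 4.5-4.7, σ 0.4-0.5 and r 0.3-0.6, the extremes are:

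- Lowest (μ 4.5, σ 0.4, r 0.6): a = 0.7/0.4 = 1.75 and Φ(a) = 0.9599. For c = 5.2, Φ₂ = 0.9315 and p = 0.030. For c = 5.5, b = 2.5, Φ₂ = 0.9567 and p = 0.003.
- Highest (μ 4.7, σ 0.5, r 0.3): a = 0.5/0.5 = 1.0 and Φ(a) = 0.8413. For c = 5.2, Φ₂ = 0.7281 and p = 0.134. For c = 5.5, b = 1.6, Φ₂ = 0.8052 and p = 0.043.

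| Level at randomization | p | Expected of 36 (36p) | Expected of 18 treated (18p) | At least one of 18: 1 − (1 − p)^18 |
|---|---|---|---|---|
| above 5.2 | 3%-13% | 1.1-4.8 | 0.5-2.4 | 42%-93% |
| above 5.5 | 0.3%-4.3% | 0.1-1.5 | 0.06-0.8 | 6%-55% |

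The first row measures how often the entry limit would be passed over. The second is the relevant one for interruption of 25 mg and for the hyperkalemia outcome.

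**The case against.** The strongest reply is that the protocol is silent and does not direct anyone to randomize such a subject. No blinding is described, so an investigator who sees a high result can decline to proceed. Screening labs could be read broadly as any panel before allocation, and the wording about one occasion most naturally means that a single valid high value excludes without confirmation. Early chemistry checks, the interruption rule and access to a nephrologist and a transplant pharmacist limit the harm. Testing eligibility at screening is a common design.

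Much of this is fair, and it limits the point to what the text permits. It does not close the gap. The calendar separates Screening from Randomization, nothing ties the later result to entry, and the safeguards in Section 8 act only after the drug has started.

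It can also be said that the damaged CHEM-7 row might be misaligned, so that a mark at randomization is not certain. As the row stands, its six marks fall under the first six columns, which include Randomization. If that reading were wrong, the interval would contain no protocol-scheduled potassium, and the entry decision would still rest on the older value.

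Three stronger readings are tempting, and the documents do not support them:

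- *The protocol contradicts itself.* It does not. The entry limit (5.2) is stricter than the interruption level (5.5), and no rule admits a subject at a value that another rule forbids. What is missing is a rule for the later sample.
- *Hyperkalemia is inflated in the treated arm only.* Raised values before allocation fall in either arm by chance, and the outcome is not restricted to treated subjects. Only interruption or discontinuation of spironolactone is confined to one arm.
- *The creatinine clearance criterion has the same defect.* That criterion carries no screening-labs wording, so the argument does not carry over.

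**Conclusion.** The point holds as a gap between three parts of the protocol that should be reconciled: the exclusion in Section 3, the calendar in Section 6 and the elevated-potassium rules in Section 8. The text permits allocation of a subject whose most recent potassium exceeds the sponsor's own entry limit. It also leaves open whether a pre-dose value above 5.5 is an outcome event.

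The textual finding rests on reading the 45-day entry as the screening-to-randomization window and the second CHEM-7 mark as falling at randomization. It does not depend on the illustration, whose inputs are all assumed. On that illustration, passing over the entry limit would probably affect a few of the 36 subjects. Starting the drug above 5.5 would be uncommon: fewer than one treated subject expected, with a 6%-55% chance of at least one. A reader who attached the 42%-93% range to the interruption rule or to the hyperkalemia outcome would overstate the size, because that range is for values above 5.2.

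**What to change.** Reconcile the three sections without changing any threshold:

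1. In the exclusion list, state that the existing potassium limit must also be met on the non-hemolyzed CHEM-7 already scheduled at randomization.
2. In Sections 3 and 6, state that this result must be available before allocation, and show the 45 days explicitly as the interval from screening to randomization if that is what is meant.
3. In Section 5, state how a pre-dose value above 5.5 counts in the hyperkalemia outcome, with the same rule for both arms.

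This takes a few sentences and no new test. The cost is a few late screen failures or re-screens, and waiting for a chemistry result before allocation.
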